2.2.1 INCLUSION CRITERIA

1. Clients must be between the ages of 16 and 35
2. Clients must have a primary diagnosis of schizophrenia, schizoaffective disorder, schizopreniform disorder, or Unspecified Schizophrenia Spectrum or Other Psychotic disorder
3. Clients must be receiving services at one of the five FEP clinics in North Carolina (OASIS, Encompass, Eagle, SHORE, AEGIS) or FEP clinics stepdown care clinics (STEP and TIDES)
4. Clients must not have had thoughts of harming themselves in the month before enrollment
5. Clients must not have been hospitalized for psychiatric reasons in the three months before enrollment
6. Clients must have been actively engaging in psychiatric medication management in the prior month
7. Clients must have access to the internet through a phone, tablet, or computer

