4 STUDY PROCEDURES

4.1 SCREENING & BASELINE PROCEDURES

4.1.1 SCREENING PROCEDURES

For recruitment of client participants, the research study coordinator will communicate with providers and other members of the treatment team to explain the project and discuss eligibility criteria for the study. If agreed to by the clinical team at each site, the research team will review the clinical census at each clinic and/or identify potential participants (clients) via the EPIC system. Clinical team members will be asked to review their current caseloads to identify potentially eligible participants (i.e., patients who are currently receiving services at OASIS, SHORE, Encompass, Eagle, AEGIS, STEP and TIDES and are considered clinically stable without current active suicidal ideation). The study coordinator and research assistant will engage in discussion with the treatment team to help identify appropriate clients for inclusion in the project. When participants have been identified and expressed interest in participation to their clinician or other treatment provider, the research study coordinator or RA will reach out to the client in their preferred method of contact (i.e., in person at the clinic or via phone/email) to discuss the project and complete an initial screen to confirm the inclusion and exclusion criteria.

If clients self-refer (in response to flyers and/or website form), the research coordinator and PI will consult with their treatment team first before screening the client (i.e., to make sure there are no issues that prevent them from safely participating in the study).

Clinicians will be consulted prior to each contact with a prospective participant and asked to advise the research team if any prospective participant should not be contacted.

For provider and PSS participation, research staff will reach out to the five FEP clinics (OASIS, SHORE, Encompass, Eagle, and AEGIS) through the program directors. Due to the long-standing relationship and close working partnership of the PI with programs, research staff are connected to program directors. After an explanation of the study is given to the program directors, program directors will be asked to discuss the study with their team prior to research staff reaching out to each team member individually. Providers and/or PSS will then be contacted by research staff to determine if they would like to participate and be screened to determine eligibility.

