Clinical safety. Clinical risk will be managed through manual and automated procedures. Information related to clinical risk will be screened twice daily by moderators (in the morning and late afternoon/evening). This information can include: 1) post made by participants, which disclose evidence of psychotic, depressive or suicidal symptoms; 2) participants reports or complaints of posts made by other users; 3) risk or self-harm related words automatically detected and blocked by the system; and 4) presence of Early Warning Signs of relapse detected by the regular monitoring of psychotic symptoms implemented within Horyzons.

Any detected increased risk will activate the Horyzons crisis protocol which includes a number of potential actions. Initially, the moderator will conduct a risk assessment based upon available information, inform the research team, and emergency contact nominated by the participant, and liaise with suitable emergency services where necessary. In addition, the system incorporates visible emergency guidelines and contact information (i.e., on every webpage).

An automated keyword system has also been built in Horyzons which will be activated each time a participant posts a contribution containing the words or phrases: suicide, die, kill myself/you/him/her/them, hang myself/you/him/her/them, harm myself/you/him/her/them, snort, shoot up, burn myself/you/him/her/them, cut myself, drown myself/you/him/her/them, stab myself/you/him/her/them, slit, slice, electrocute, shoot myself/you/him/her/them, top myself, jump in front of, jump off, end it all, sleep and never wake up, death, die, asphyxiate, or gas. When these words are detected, the contribution will be blocked and the participant will be sent an automated message explaining that the content has been blocked and if they are facing distress then they should contact the emergency contact number as soon possible or if they are not facing distress, they may like to consider rephrasing their post. An automated message will also be sent to the Horyzons moderator containing the attempted post.

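### Read literally, the self-harm keyword list fires on *suicide* and *kill myself* but not on *suicidal* or the -ing forms of its self-directed phrases, and the matching rule is not stated

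*Combined protocol and SAP*

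**What the plan says.** The Clinical safety part of section 6.1 manages risk by manual and automated means. Moderators screen risk information twice a day. One item in that screen is posts "which disclose evidence of psychotic, depressive or suicidal symptoms". A separate item is "risk or self-harm related words automatically detected and blocked by the system". A fourth is "presence of Early Warning Signs of relapse detected by the regular monitoring of psychotic symptoms implemented within Horyzons".

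The automated part is a filter "which will be activated each time a participant posts a contribution containing the words or phrases: suicide, die, kill myself/you/him/her/them", and the list then continues to its end. It is closed: nothing marks the terms as examples, and stemming, wildcards and word variants are not mentioned. On a hit, "the contribution will be blocked and the participant will be sent an automated message explaining that the content has been blocked". That message points a distressed client to the emergency number and invites anyone else to rephrase. Finally, "An automated message will also be sent to the Horyzons moderator containing the attempted post".

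Section 6.1 also gives users a report function and puts emergency information on every page.

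**The concern.** The filter is the only safeguard described that reacts to the content of a post at the moment of posting. A list of base forms matched literally lets through ordinary ways of voicing the same thought. A client who writes *I am going to kill myself* is blocked, prompted and flagged. One who writes *I feel suicidal tonight* or *I keep thinking about killing myself* is not.

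Three things are at stake for such a post: the immediate prompt to its author, the block that keeps it from other clients, and the alert that brings it to a moderator. Entry screening reduces the risk ("Clients must not have had thoughts of harming themselves in the month before enrollment", section 2.2.1) but looks back one month, while access lasts about 12 months (section 2.1). This is a participant-safety point. No study analysis depends on it.

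**Working it through.** The plan gives no figure to reproduce. The check is a count on the list printed in section 6.1.

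**Step 1: expand the list.** Seven verbs (kill, hang, harm, burn, drown, stab, shoot) each take five objects (myself, you, him, her, them): 7 × 5 = 35 phrases. Seven more phrases are *shoot up*, *cut myself*, *top myself*, *jump in front of*, *jump off*, *end it all* and *sleep and never wake up*: 35 + 7 = 42. Single words are *suicide*, *die*, *snort*, *slit*, *slice*, *electrocute*, *death*, *asphyxiate* and *gas*: 9. Total 42 + 9 = 51 distinct entries (*die* is printed twice).

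**Step 2: pick the self-directed phrases.** Nine contain *myself* (the seven verbs plus cut and top). Four more are *end it all*, *sleep and never wake up*, *jump in front of* and *jump off*. Total 13.

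**Step 3: test each form under two literal rules.** Substring matching fires if the entry occurs anywhere in the text. Whole-word matching fires only if it stands as a complete word or phrase.

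| Form | Substring | Whole word |
|---|---|---|
| 13 base forms | 13 of 13 | 13 of 13 |
| 13 -ing forms | 0 of 13 | 0 of 13 |
| *suicidal* | no | no |

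*Suicide* does not catch *suicidal* even as a substring, because the spelling changes after *suicid*. The -ing ending breaks each phrase in the same way. For these forms the result does not depend on which rule is used. A post would still fire if it also held another listed term.

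**Step 4: the rule matters in the other direction.** *Die* fires inside *diet*, *studies* and *audience* under substring matching, and in none of them under whole-word matching. The printed text does not say which applies.

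**Step 5: effect of adding the missing forms.** Adding *suicidal* and the 13 -ing forms gives at most 1 + 13 = 14 new entries. I tried eight constructed posts, none of which fires on the current list.

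- Risk posts: *I feel suicidal tonight*; *I keep thinking about killing myself*; *I have thoughts of harming myself*. After the addition, 3 of 3 fire.
- Recovery or idiom posts: *I used to feel suicidal but not now*; *I stopped cutting myself a year ago*; *cut him some slack*; *I was dead tired after work*; *I am dying to see that film*. After the addition, the first two fire: 2 of 5.

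These posts illustrate the trade-off. They are not a sample of what clients write.

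**The case against.** **The live rule is unknown.** The protocol describes a system already built and does not give its matching rule. Stem or variant matching is neither stated nor excluded. The synopsis says the clinic directors approved the safety measures, and the safety plan itself is not in the document. This stands. What the text establishes is a closed list with no stated rule; a gap in the running filter is conditional.

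**Manual detection is already planned.** The twice-daily screen covers posts showing suicidal symptoms separately from keyword hits. Moderators review the social space (section 2.1, Expert Moderation), users can report any post, and there are at most 50 clients. This also stands. A reader might infer that such posts would go undetected, and the documents do not support that.

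**A slower human response is not shown.** A reader might infer one, but keyword hits go into the same twice-daily screen, and no response to an alert outside moderation sessions is described. Limits on moderator cover apply to hits as well as misses.

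**The protocol's own vocabulary proves little.** It is tempting to note that the list misses terms the protocol uses itself, as in "are considered clinically stable without current active suicidal ideation" (section 4.1.1). Those are staff-facing words and say little about how clients write.

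**Some variants add little.** Past-tense forms such as *topped myself* or *jumped off* are weak signs of current risk, so I do not count them in the core point.

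None of this removes the narrower loss of immediate block, prompt and alert if the list is applied as printed. Page-level emergency links soften the loss of the prompt, but they do not respond to what the client wrote.

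**Conclusion.** The point holds for the printed list. *Suicidal* and all 13 -ing forms of the self-directed phrases do not fire under either literal rule, while all 13 base forms do. If the system works as written, posts using only those forms get no block, no prompt and no moderator alert, and rest on the manual screen, user reports and static links.

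This assumes literal matching, which the documents neither confirm nor rule out. No document gives a miss rate, and none should be inferred from 0 of 13. If the live filter already handles variants, what remains is to state the rule and record a test. The change is worth making because it is cheap and concerns a suicide-risk safeguard.

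**What to change.** Run *suicidal* and the -ing forms of the 13 self-directed phrases through the live filter and keep the result. Add those that fail to the list in section 6.1 as explicit entries, at most 14, with the action already described: block, message inviting a call or a rephrasing, and moderator alert. Explicit entries work under either matching rule. State the matching rule in the same place, which also settles whether *die* is meant to block *diet*.

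Past-tense forms, *dying*, and a separate tier that alerts without blocking are optional choices for the study team. The tier would be new software behaviour, since the protocol describes one action for every hit, and it would leave the post visible to peers.

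Cost: a short test, up to 14 entries and one sentence of protocol text. Section 6.4 refers to a team that developed the application, so a request to them may be needed. Some recovery or harmless posts will be blocked and need rephrasing. The plan already accepts that cost for *die*, *death* and *gas*, but it does bear on the self-disclosure that section 1 counts as a benefit.

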6.2 NON-SIGNIFICANT RISK DOCUMENTATION

The present study has been deemed of non-significant risk (NSR) to participants.

6.3 POTENTIAL BENEFITS OF THE RESEARCH TO SUBJECTS AND OTHERS

While the field is still in its infancy, there is preliminary evidence that online interventions that combine therapy, social networking opportunities and expert and peer moderation may be better received by individuals with first episode psychosis than less integrated approaches. The proposed study will expand this growing body of work by testing the clinical utility and ability to implement the intervention as part of mental health care at first episode clinics in North Carolina.

Benefits to clients. The proposed study may increase clients' sense of belonging and social support. Also, if they engage in therapeutic pathways within the Horyzons platform, they might develop cognitive behavioral and mindfulness-based skills.

Benefits to providers. Clinicians and peer support specialists may gain insight into clients' experiences using the platform, including possible barriers to engagement and challenges to disseminating the Horyzons platform within the clinic. This information may prove useful to clinicians and PSSs as they consider ways to incorporate online interventions and other adjunct services into their existing treatment approaches in the future.

6.4 CONFIDENTIALITY OF DATA

Names and associated contact information for potential subjects during the recruitment phase will be stored in a manner similar to that used to store study data. This information will be kept in a locked file cabinet in a locked office in the Department of Psychology and Neuroscience at UNC or within the administrative or secure storage areas of the FEP clinics involved in this project. Contact information will be destroyed immediately after it is ascertained that an individual does not want to participate in the study. Declining participants' names will be retained on a secure password protected network to ensure that the same participant is not contacted more than once regarding participation.

A member of the research team will meet individually with the client in order to explain the components of the Horyzons platform, elicit and answer any questions the client may have, and obtain informed consent. We will also collect information about current suicidal ideation and stability (e.g., recent hospitalizations) to assess eligibility for participation. Persons will also be creating a Horyzons profile and answering questions about character strengths (e.g., curiosity, love of learning), which are embedded in the Horyzons platform. These data will be linked to other sources of information, including the record of their interactions within the Horyzons system (e.g., number of posts/comments on the community page).

The Horyzons system and data generated by users of Horyzons will be hosted on a secure web server. A range of measures are in place to ensure the security of the Horyzons website and the data generated by users. In addition, the team who developed the web application has placed measures within the application to secure the application and database against unauthorized access. These measures conform to industry best practice as defined by the Open Web Application Security Project (www.OWASP.org). Qualitative interviews will be conducted via secure Zoom, and will be digitally recorded (via Zoom or using audio recorders) for the purposes of transcription. These recordings and transcripts will be immediately uploaded to a secure, password-protected server and deleted from local devices. The project electronic database (including all transcripts from interviews) will be password protected and stored securely, and will only be directly accessible by the research study coordinators, clinicians and peer support specialists, and collaborators involved in this project, or PI ([name]).

As this research program is being implemented in clinical settings, it is possible that FEP clinicians or PSSs will create notes that indicate the participant is involved in the project, describe any issues may arise, etc. that will be connected to their medical record. These documents will be stored in approved medical record systems on HIPAA-compliant computers. If researchers complete inductions or introductions to the site via video conference, the video or audio from these interviews will not be saved or recorded. Audio from qualitative interviews will be stored on a secure, password-protected server.

Identifiable data will only be shared with the providers and PSSs of subjects in the study with the permission of the subjects (obtained during informed consent). Clinicians will be contacted if issues arise related to safety during the trial. As part of the informed consent process, all subjects will provide the name and contact info of a clinician that

we may contact if we become concerned about their safety (e.g., physical and/or mental health) during the course of the trial. We will not be sharing any confidential information with anybody outside of these providers and PSSs.

Identifiable data will be maintained for 5 years following study completion. At that point, hard copies of identifiable data including consent forms and contact information will be shredded. Electronic data will be de-identified upon entry, with the exception of the subjects' birth dates for the purposes of calculating their exact age.

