Safe and informed orientation to the system will be a priority for the research team. Peer support specialists, clinicians, research coordinator, and/or a graduate student in the Department of Psychology and Neuroscience at UNC-CH will meet with each participant to provide them with login information, help set up their account and orient them to the Horyzons system, including details of the terms of use. All users of Horyzons will be asked to nominate an emergency contact person, such as a close family member. The terms of use explain to users that information passed onto moderators or communicated within the system that may indicate concerns regarding their wellbeing may be communicated with their treating team or private practitioner. Hard copies of 'Horyzons Terms of Use' will be provided to users which will be made available online and in printed form. Participants will be required to sign the hard copy as well as accepting the terms of use on entry into the system. The system also includes a "report function" which enables users at any time to indicate to the moderator a concern about any material posted by a user, including concern about potential abuse or concerns about the wellbeing of another participant. The moderator will assess the basis of the report and respond accordingly, which can include the removal of the material or deactivation of an account.

In addition, users will be able to "switch off" their profile and hide all of their existing comments on the system should they become concerned about their privacy during their course of participation. The limits of the moderator's ability to respond (e.g., in a timely manner to emergencies) will also be fully explained. In order to protect the privacy of users who discontinue using the system, any accounts that have not been activated for one month may be deactivated following a follow-up telephone call from the moderator. Specifically, our disengagement protocol is such that a participant will receive an email/call/text message if they have not logged onto the platform for two weeks. If another two weeks pass, we will call this person to check in about any potential issues or concerns. If participants do not comply with the guidelines for safe use of Horyzons (e.g., discriminatory comments towards other users) they will be excluded from the system.

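### Section 6.4 forbids sharing confidential information beyond providers and PSSs, with no emergency exception, yet the 6.1 crisis protocol sends it to the nominated emergency contact and emergency services

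*Combined protocol and SAP*

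**What the plan says.** Section 6.4 (Confidentiality of Data) deals with sharing in one short paragraph. It first limits recipients and ties sharing to consent: "Identifiable data will only be shared with the providers and PSSs of subjects in the study with the permission of the subjects". It then turns to safety: "Clinicians will be contacted if issues arise related to safety during the trial". To make that possible, it asks each participant to name a clinician: "As part of the informed consent process, all subjects will provide the name and contact info of a clinician that" staff may approach if they become worried about the participant's safety. The paragraph ends: "We will not be sharing any confidential information with anybody outside of these providers and PSSs".

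Section 6.1 (Monitoring Risks) provides for a different contact. Under Online safety: "All users of Horyzons will be asked to nominate an emergency contact person, such as a close family member". Under Clinical safety: "Any detected increased risk will activate the Horyzons crisis protocol which includes a number of potential actions". The steps listed there begin with the moderator's own risk assessment. The moderator is then to "inform the research team, and emergency contact nominated by the participant, and liaise with suitable emergency services where necessary".

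Section 6.1 also summarises the Horyzons Terms of Use. According to that summary, users are told that information indicating "concerns regarding their wellbeing may be communicated with their treating team or private practitioner".

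**The concern.** The two sections give a moderator opposite instructions on the same event. Section 6.1 directs disclosure to a person and to services that 6.4 places off limits. The closing sentence of 6.4 comes straight after that section's own safety provision, so it cannot easily be read as being only about routine data handling. Safety contact is raised there, is limited to clinicians, and the list of recipients is then closed.

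Participant protection is at stake; no estimate is. The material screened under 6.1 includes posts showing suicidal, depressive or psychotic symptoms, and the clients all have psychotic disorders. A moderator who follows 6.1 departs from a written confidentiality commitment. One who follows 6.4 leaves out two steps meant to protect the client. Moderators include peer support specialists and graduate students as well as clinicians (sections 2.1 and 6.1), and they should have one rule to follow when time is short.

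**Working it through.** No arithmetic beyond a count applies, so the check sets the two provisions side by side and then looks for an exception elsewhere.

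**Step 1: who may receive confidential information under 6.4.** The clients' providers and PSSs, and nobody else. The sentence carries no qualifier for emergencies.

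**Step 2: who receives it under the 6.1 crisis protocol.**

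| Recipient named in 6.1 | Within the 6.4 group? |
|---|---|
| Research team | Not in conflict: the team is the party making the 6.4 promise, so informing it is internal |
| Emergency contact nominated by the participant | No, for a relative, which is the example 6.1 gives |
| Emergency services, where necessary | No |

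The count is 2 of 3 recipients outside the permitted group. Telling either of them that an identified client has shown signs of suicidal or psychotic symptoms passes on confidential information.

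**Step 3: is the emergency contact the same person as the 6.4 safety contact?** No. Section 6.4 asks for a clinician during consent. Section 6.1 asks for an emergency contact and gives a family member as its example. Section 6.4 does not mention the second contact.

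**Step 4: does any other section supply an exception?**

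- *Section 6.1, Terms of Use summary:* names the treating team or a private practitioner as recipients of wellbeing concerns. It lists neither the emergency contact nor emergency services.
- *Section 6.1, emergency link on each page:* gives users emergency and crisis numbers to call themselves. It does not authorise staff to disclose.
- *Section 2.1, Treatment Period:* provides for sharing clinical information with the client's clinical team, which is already within 6.4.
- *Section 7.1:* routes deterioration to the treatment team and the principal investigator, with concerns about adverse events going to the IRB.
- *Sections 7.2 and 7.3:* cover reporting of serious adverse events and deaths, with no exception to 6.4.
- *Section 9:* describes the consent process, again with no exception.

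**Step 5: reach.** Section 2.2 allows up to 50 clients, each with access for about 12 months. That is the number of people the rule covers. It does not measure how often the rule would be broken, and the protocol gives no rate of crisis activations from which to estimate one.

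**The case against.** The strongest reply is that a specific rule governs over a general one. Section 6.4 is mostly about storage, servers, recordings and retention, while 6.1 is the provision written for crises, and sensible staff would follow 6.1. That is probably what would happen. It is a reason to make the text match the intended practice, because the protocol nowhere says that 6.1 prevails.

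Second, the participant chooses the emergency contact, which suggests agreement to that person being called. The inference is fair, but 6.4 ties permission to sharing with providers and PSSs only. Nor does the inference reach emergency services.

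Third, the crisis steps are described as possible actions, emergency services are involved only where necessary, and a relative is only an example of an emergency contact. All of this stands as a limit on how often the conflict would arise. A nominated contact who happened to be a provider would raise no conflict. Emergency services and family contacts still do, and an optional step is still a planned one.

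Fourth, so literal a reading might also catch the reports to the IRB and the serious-adverse-event and death reports in section 7. The documents do not show that those reports carry identifiable data to outsiders, so they neither defeat the point nor clearly need the same exception.

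Last, the consent form may already contain an exception. Consent pages were removed from the material reviewed and the full Terms of Use are not supplied, so nothing is claimed about either. The protocol's own text would remain inconsistent.

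**Conclusion.** The concern holds as a contradiction within the protocol. Followed literally, the last sentence of 6.4 gives the wrong result on a safety step: it excludes two of the three recipients that the crisis protocol names. It should be corrected, but the point should be kept in proportion. It changes no endpoint, analysis or sample size, it takes effect only when one of the two steps is taken, and its frequency is unknown.

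The conclusion rests on two readings: that a nominated emergency contact will usually be someone other than a provider or PSS, as the protocol's own example suggests, and that news of a client's risk state is confidential information. For emergency services, only the second is needed.

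**What to change.** Keep the last sentence of 6.4 and add an exception to it, for example: *except that, when the Horyzons crisis protocol is activated, relevant risk information may be given to the participant's nominated emergency contact and to emergency services.* This is narrow by design. It is limited to an activated crisis protocol, to information relevant to the risk, and to the two recipients that 6.1 already names, so it permits no disclosure that the protocol does not already plan.

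Then check that the consent form and the Horyzons Terms of Use state the same exception, and align them if they do not.

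The cost is one sentence, a check of two documents and one IRB amendment. The only drawback is that the confidentiality statement becomes less absolute.
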